### **4. Participant Selection, Enrollment, and Withdrawal**

#### **Study Population**

We aim to enroll 230 subjects including subjects diagnosed with keratoconus or glaucoma (115 in each cohort). There will be no enrollment restrictions based on gender, ethnic origin or HIV status and the study population will reflect the demographics of NYU Department of Ophthalmology.

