## Keratoconus and IOP Elevation Study

As part of the routine examination, pupils will be dilated using dilating drops (tropicamide and/or phenylephrine hydrochloride). As part of routine clinical IOP measurement, numbing drops (proparacaine) will be used. In cases where the clinical evaluation did not include pupil dilation and pupil size prevents ocular imaging, dilating drops might be used for the purpose of imaging in the study.

All procedures will be performed by clinical or research staff.

**Experimental procedure:** The IOP will be measured with the Goldman applanation tonometer, and then the IOP will be increased using an ODM. Proparacaine drops, which are widely used during routine eye examinations, will be used during this procedure to numb the eye while the IOP is measured. ODM is an FDA approved device that allows an increase of force on the eye in a controlled fashion and is routinely used as part of neurophthalmic evaluation. Forces will be imposed on the eye while Goldman tonometry is used to measure the IOP to reach the target IOP between 20-35 mmHg. The procedure will take five minutes.

OCT scanning will be obtained at baseline and with increased IOP. The IOP elevation will last no longer than two minutes, during which scans will be acquired by the imaging device. This stage will take 10 minutes.

The subject will be tested by clinical or research staff under the direct supervision and direction of the principal investigator or co-investigators. All devices in this study are FDA-approved with the exception of the investigational OCT devices and multi-modal adaptive optics system; see Appendix). None of the systems in this study are considered investigational, nor do any of the devices produce harmful radiation.

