### Devices

#### 1. Ophthalmodynamometer

The ODM (Baillart ophthalmodynamometer, W. Koch Optik, Zurich, Switzerland) is a disc attached to a piston that induces a controlled force on a fixed area. The device will be used to apply a pressure within the range of 20 mmHg - 35 mmHg 4 times to each eye. Each increase of pressure will last approximately 30 seconds. The device is FDA approved and will be used as routinely used in clinical practice.

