### 6. Statistical Plan

The data will be divided into two groups according to the clinical diagnosis: subjects with keratoconus and with glaucoma. Baseline ONH location and shape will be compared to IOP stressed location and shape by mixed effect models.

Based on unpublished pilot data, an increase in cup depth of approximately  $13\mu\text{m}$  in response to acute IOP elevation is anticipated. To detect a difference of  $13\mu\text{m}$  in cup depth with an experimental error of  $0.07\mu\text{m}$ , a sample of 230 subjects with keratoconus and glaucoma has a power of 80% (5% level of significance).

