## **7. Safety and Adverse Events**

### **Risks and Discomforts**

There is a risk of blurred vision and difficulty in near vision operation (e.g., reading and writing), which is common, due to the use of dilating drops (tropicamide and/or phenylephrine hydrochloride). The effects of these drops will disappear within 3-4 hours after instillation. The participant may be asked to remain in the clinic in the event that they experience blurred vision and do not have an accompanying person.

Pupil dilation may cause an increase in eye pressure or the possibility of an angle-closure event, which happens in a rare configuration of eyes. All subjects will be examined clinically before dilating drops are instilled to identify eyes at risk, in which case no dilation drops will be used. If either of these risks should occur, the subject will be treated immediately with eye drops at no cost. There is a rare risk of an allergic reaction to the drops, as with any drug or medication.

Ophthalmologic OCT imaging is performed in a non-contact fashion, so there is minimal risk of infection to the participant. To reduce the possibility of eye infection, all exposed surfaces near the eye, as well as the chin rest and forehead rest of the instrument, will be cleaned with alcohol before participants are examined. The risk of infection is low.

Imaging will be performed using commercial (FDA approved) and non-commercial (non-FDA approved) imaging instruments. All devices are subject to standard medical regulatory and safety requirements and adhere to the American National Standards Institute safety standards for the use and exposure to lasers. There is no known cumulative risk for repeating OCT scans multiple times on the same day or on different days.

Infrequent risks from the IOP elevation using the ODM include corneal abrasion. However, the ODM is designed with a smooth surface to minimize this risk. While increasing IOP causes neural loss, the length and magnitude of the pressure elevation in our study design was previously used and have been shown to not cause any short or long-term damage.

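### The 80% power is attached to all 230 enrolled subjects with no allowance for unusable scans, and no baseline-scan acceptability rule precedes the four pressure loadings

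*Combined protocol and SAP*

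**What the plan says.** - **Enrolment.** Section 4, Study Population: "We aim to enroll 230 subjects including subjects diagnosed with keratoconus or glaucoma (115 in each cohort").
- **Power.** Section 6 anticipates a cup-depth increase of about 13 µm "in response to acute IOP elevation is anticipated". It then asserts that, for a 13 µm difference "in cup depth with an experimental error of" 0.07 µm, "a sample of 230 subjects with keratoconus and glaucoma has a power of 80"% ("5% level of significance"). It mentions no loss.
- **Outcome.** Under Analysis Methods in Section 6, the deformation measures come from OCT images. The Statistical Plan compares baseline with the pressure-stressed state. Mixed models allow for both eyes in some subjects.
- **Loading.** Section 5 obtains OCT at baseline and under raised pressure. Its ophthalmodynamometer (ODM) entry says the device will "apply a pressure within the range of 20 mmHg - 35 mmHg 4 times to each eye".
- **Checks on imaging.** The exclusion criteria in Section 4 remove media opacity, cornea included, and conditions that prevent fixation. Section 5 adds that where the clinical examination did not include dilation and "pupil size prevents ocular imaging, dilating drops might be used for the purpose of imaging in the study". Section 7, Risks and Discomforts, has every subject examined before drops "to identify eyes at risk, in which case no dilation drops will be used".
- **Not found in the text.** There is no quality threshold for the baseline scan, no rule linking that scan to the decision to load, and no account of how unusable scans are handled.

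**The concern.** The powered measure is a change in cup depth, so an eye contributes only if both of its scans can be measured. Using one number for enrolled and analysable subjects leaves no room for scans that fail, and the plan itself recognises that imaging can fail. Two things are at stake.

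- **Power.** Whatever power the design truly has at 230 analysable subjects, it has less at 230 enrolled if some yield no pair. The reader is not told how much less.
- **Exposure without return.** Section 7 names corneal abrasion as an infrequent risk of the loading and acknowledges that raised pressure can cause neural loss, although it holds that this magnitude and duration are harmless. The adverse-event section says subjects gain no direct benefit. Loading an eye whose baseline scan is already unusable carries that risk and cannot yield a change score. The baseline scan could reveal this first, but the plan does not say it is looked at for that purpose.

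**Working it through.** **1. Can the plan's 80% be reproduced?**

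Inputs from Section 6: difference 13 µm, error 0.07 µm, N = 230 (115 per cohort, Section 4), 5% level. Sidedness is not stated; two-sided is assumed.

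- As printed: 13 / 0.07 ≈ 186 standard deviations. Power is about 100%, whether for two groups of 115 or for a paired test on 230, and stays there in the two-group calculation even at 50% loss. The 80% is not reproduced.
- Standard deviation that would give 80%, from SD = 13 / [(1.960 + 0.842) × √(2/115)] for two groups: 35.2 µm. For a paired test on 230, SD = 13 × √230 / 2.802 = 70.4 µm.
- If 0.07 were in millimetres (70 µm), a two-sided paired t-test needs exactly 230 subjects (power 80.1%). This is inferred from the arithmetic; the documents do not say it. On that reading, 230 is the analysable number with none spare.

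**2. Effect of loss, taking 80% at 230 as correct**

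The documents give no rate of unusable scans, so the range is assumed. With loss d equal in both cohorts and usable share f = 1 − d:

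Power = Φ(2.802 × √f − 1.960)

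| Assumed loss | 2.802√f − 1.960 | Power | Paired t, SD 70 µm (analysable n) | Enrolment to keep 230 analysable, 230/(1 − d) |
|---|---|---|---|---|
| 0% | 0.842 | 80% | 80.1% (230) | 230 |
| 5% | 0.771 | 78% | 77.9% (218) | 243 |
| 10% | 0.698 | 76% | 75.8% (207) | 256 |
| 20% | 0.546 | 71% | 70.7% (184) | 288 |

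The two power columns agree because both start from 80% at 230. They count whole subjects lost and ignore any information from a second eye.

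**3. Can an eye be loaded without a usable baseline scan?**

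- Section 4 screens media and fixation. It does not test whether the scan itself is measurable.
- Section 5 answers a small pupil with drops that might be used. Section 7 withholds drops from eyes at risk. An eye that is both has no stated route to an adequate image.
- The ODM entry then applies the loadings to each eye without reference to the baseline scan.

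Read together, these sections permit the loading of an eye with an unusable baseline scan. They do not say how often this would happen.

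**The case against.** **The power claim.** On the printed inputs power is about 100% whatever the loss, so a reader who infers that the stated power is overstated has not shown it from those inputs. That stands, and it is why the figures above are conditional. It does not show that loss is harmless, because the same inputs cannot produce the plan's own 80%.

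**Checks do exist.** A reader might infer that nothing protects against unreadable eyes. That is wrong: media opacity and fixation exclusions, dilation for imaging, and a baseline OCT all bear on it. Section 7 calls the eyes at risk of angle closure rare. What is missing is narrower: a decision rule on the baseline scan before loading.

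**Silence is not instruction.** The plan does not direct staff to load an unreadable eye, and they may well not do so. The device appendices cited in Section 5 are not in the text reviewed and may contain scan-quality rules. Both limit the point to what the text leaves open.

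**Second eyes and a short session.** One failed eye need not lose the subject, and loading and scanning take minutes, so ordinary dropout should be small. This stands. The offset cannot be sized, because neither the proportion with two eyes nor the between-eye correlation is given.

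**Selection between cohorts.** Glaucoma eyes are chosen on the optic nerve head or nerve fibre layer and on visual fields, keratoconus eyes on the cornea. A reader might infer that readability differs by cohort and biases the contrast. The documents give no readability rate, no response SD and no link between cup depth and response, so no size can be put on this. The powered measure is cup depth, which may be measurable where the lamina is not. Reweighting the readable eyes is no remedy: the cup depth and rim area it would need come from OCT and would be missing in the unreadable eyes.

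**Conclusion.** The point holds in a limited form. Enrolled and powered numbers are both 230 with no allowance for loss, and no acceptability rule on the baseline scan precedes the four loadings.

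If 80% at 230 analysable subjects is accepted, power is about 78%, 76% and 71% at 5%, 10% and 20% loss. This rests on assumed loss rates, equal loss in the cohorts, a two-sided 5% test and no offset from second eyes. It is not a finding that the trial has less than 80% power: the true figure is unknown until the inputs in Section 6 are corrected.

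That some eyes would be loaded to no purpose is a possibility the text leaves open; its frequency cannot be stated. Neither a bias between the cohorts nor an absence of all readability checks is supported. The point is worth acting on because the remedy uses a scan that is already planned.

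**What to change.** 1. **Section 5.** Before the first loading, grade the baseline OCT against one written acceptability threshold for cup depth, identical in both cohorts. Take only eyes that meet it into the loading stage. Log the others with the reason, and report their number by cohort.
2. **Section 6.** First correct the inputs: state the unit and meaning of the experimental error and name the test being powered, since 13 µm and 0.07 µm do not give 80%. Then say that the power applies to subjects with an analysable pair, and give the power for 230 enrolled over a stated range of loss, as in the table. State how unusable scans and second eyes enter the analysis.

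**Cost.** Wording in two sections and roughly a minute per eye to grade a scan already being taken. The stated power may look slightly less favourable. No further subjects are needed unless the sponsor wants 230 analysable, in which case enrolment would be 243, 256 or 288 at 5%, 10% or 20% loss.

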### Analysis Methods

The ONH and peripapillary region scans by OCT will be evaluated for tissue deformation, decrease in the rim area, increase in cup depth and changes in the lamina cribrosa structure. . Outcome measures will evaluate the aforementioned expected deformations of the LC in microns. These micron measurements will be obtained from in vivo OCT images. Cornea will be evaluated for anterior and posterior curvatures, aberrations, pachymetry and hysteresis.

Mixed effect models will be used for longitudinal analysis accounting for the use of information from both eyes for some subjects. Custom analysis techniques will be utilized to measure differences in ocular structures, especially the LC, under different pressure conditions.

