## Keratoconus and IOP Elevation Study

### Study Summary

Title	Optic Nerve Head Structural Response to IOP Elevation in Patients with Keratoconus
Short Title	Keratoconus and IOP elevation Study
IRB Number	17-01360
Study Type	Human study
Study Design	Prospective experimental study
Study Intervention	In-vivo investigation of ocular structure in eyes with keratoconus under elevated intraocular pressure
Study Duration	Indefinite
Study Location(s)	NYU Department of Ophthalmology: Faculty Group Practice
Primary Objective	To examine in-vivo how lamina cribrosa in subjects with keratoconus respond to increasing intraocular pressure
Sample Size	230 subjects
Diagnosis and Main Inclusion Criteria	Subjects diagnosed with keratoconus or glaucoma
Control / Comparison	None
Statistical Methodology	Mixed effect models for the comparison between keratoconus and glaucomatous eyes

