### **2. Study Objectives**

To study the differences in optic nerve microstructure and biomechanical features between keratoconus and glaucomatous eyes. We hypothesize that subjects with keratoconus have an abnormal biomechanical response of the lamina cribrosa in response to IOP modulation.

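### The only power figure is for cup depth, an unjustified stand-in for the lamina cribrosa response, and no primary outcome or contrast is named

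*Combined protocol and SAP*

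**What the plan says.** The Study Summary gives the primary objective as "To examine in-vivo how lamina cribrosa in subjects with keratoconus respond to increasing intraocular pressure" and the methodology as "Mixed effect models for the comparison between keratoconus and glaucomatous eyes". Section 2 adds: "We hypothesize that subjects with keratoconus have an abnormal biomechanical response of the lamina cribrosa in response to IOP modulation".

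Section 6 (Statistical Plan) describes a within-eye comparison: "Baseline ONH location and shape will be compared to IOP stressed location and shape by mixed effect models". Its sample-size paragraph begins "Based on unpublished pilot data, an increase in cup depth of approximately" 13 µm. It then claims 80% power at the 5% level for a 13 µm difference in cup depth, with an experimental error printed as 0.07 µm and 230 subjects. Section 4 splits these as 115 per cohort.

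Analysis Methods says the scans will be assessed for tissue deformation, "decrease in the rim area, increase in cup depth and changes in the lamina cribrosa structure", and continues: "Outcome measures will evaluate the aforementioned expected deformations of the LC in microns". Four groups of corneal measures follow. No outcome is called primary, secondary or exploratory, no multiplicity rule is given, and no effect size, SD or power is stated for any LC measure.

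**The concern.** The question the study exists to answer and the quantity it was sized on are not the same. The objective is about the LC. The power is for cup depth, and the list in Analysis Methods treats cup depth and LC structure as separate items. It is also unclear whether the 13 µm is a change from baseline or a difference between cohorts, although the planned comparison is between cohorts.

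Two things are at stake. First, a reader cannot tell what LC difference 115 per cohort could detect with reasonable power, so a null LC result would be hard to interpret. Second, with several optic nerve head outcomes and no order among them, a positive finding on any one could be presented as support for the hypothesis, and the error rate of that claim is undefined.

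**Working it through.** **Inputs from the plan.** Difference 13 µm; experimental error 0.07 µm (not stated whether SD, standard error or measurement error); N = 230, 115 per cohort; power 80%; level 5%, sidedness not stated. I use two-sided 5%, so z₀.₉₇₅ + z₀.₈₀ = 1.960 + 0.842 = 2.802.

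**1. The plan's own figure.** Taking 0.07 µm as an SD, the effect is 13 / 0.07 ≈ 186 SDs. Power at 115 per cohort is then essentially 100% and the formula returns 1 subject per group. The stated 80% at 230 does not reproduce.

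**2. What would reproduce it.**
- Two cohorts of 115: 80% power for 13 µm requires SD = 13 / (2.802 × √(2/115)) = 13 / 0.3695 ≈ 35.2 µm, a value that appears nowhere in the plan.
- One-sample change from baseline, all 230 pooled, with 0.07 read as 0.07 mm = 70 µm: n = (70 × 2.802 / 13)² = 227.6, so 228 by the normal formula; the t-test version gives 229.5, so 230, with power 80.1%.

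The second is the only reading found that matches. It is an inference, and it describes a pooled within-subject change.

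**3. The between-cohort contrast on that reading.** With an SD of change of 70 µm and 115 per cohort, the standard error is 70 × √(2/115) = 9.23 µm. The expected z is 13 / 9.23 = 1.408, so power = Φ(1.408 − 1.960) ≈ 29%. Reaching 80% would need 2 × (70 × 2.802 / 13)² = 455.1, so 456 per cohort.

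**4. The LC question.** No LC effect or SD is given, so power in microns cannot be computed. In SD units, the difference detectable with 80% power is 2.802 × √(2/115) ≈ 0.37 SD. Over an assumed range of true between-cohort differences:

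| Difference (SD) | Power |
|---|---|
| 0.2 | 33% |
| 0.3 | 62% |
| 0.37 | 80% |
| 0.5 | 97% |

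**5. Error rate if every listed optic nerve head outcome were tested at 5%.** This is an assumption; the plan does not say so. For four independent tests, 1 − 0.95⁴ = 18.5%. For four tests with common correlation r and c = 1.960, the rate is 1 − ∫ φ(u) [Φ((c − √r·u)/√(1−r)) − Φ((−c − √r·u)/√(1−r))]⁴ du:

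| r | Chance of at least one false positive |
|---|---|
| 0 | 18.5% |
| 0.5 | 15.6% |
| 0.7 | 13.0% |
| 0.9 | 9.4% |

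If tissue deformation is only the general term for the other three, independence gives 1 − 0.95³ = 14.3%, and r = 0.9 gives 8.4%. The plan gives no correlations.

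**The case against.** The strongest reply is that the plan itself links cup depth to the LC. Analysis Methods calls the listed changes deformations of the LC, the Section 2 objective extends to optic nerve microstructure and biomechanics generally, and the Background aims at optic nerve head structures including the LC. That stands in part. A reader might infer that the power figure concerns something unrelated to the primary question, and the documents do not support this. What they show is a surrogate used without justification. The linking sentence does not supply one: it lists cup depth and LC structure separately, and it gathers rim area, which is an area, into a measurement in microns.

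A second reply concerns the 5% level. A reader might infer that several outcomes share an unadjusted 5%, so that the true error rate is well above it. The documents do not say this. The 5% appears once, in the cup-depth sentence. One LC outcome tested alone at 5% would keep its error at 5%, and the plan does not rule that out. So the figures in step 5 are conditional, and strong correlation shrinks them. What remains is that the plan does not name that outcome.

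Third, 70 µm is inferred, so the 29% is not an established property of the study. That is right. Equally, one should not infer that the 80% is sound for cup depth and merely needs relabelling, because the printed inputs do not yield it.

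**Conclusion.** The point holds in this form: no primary outcome or contrast is named; the sole power figure is for a cup-depth change whose role as an LC surrogate is not justified; and the remaining outcomes are neither ranked nor labelled exploratory. Power for the LC comparison is unstated and cannot be derived in microns. The firm statement is that 115 per cohort detects about 0.37 SD with 80% power, assuming one independent value per subject, two-sided 5% and no dropout.

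Two further sizes are conditional. The chance of at least one false positive is about 9% to 18.5% if all four optic nerve head outcomes are tested at 5%. Power for a 13 µm between-cohort difference is about 29% if the SD of change is 70 µm. The documents do not establish an inflated error rate or an underpowered study. They leave both undefined for the primary question. The study can still be run, but this should be corrected before analysis.

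**What to change.** **Analysis Methods.** Name one LC deformation measure in microns as primary; change in anterior LC depth is one example, and the choice is the investigators'. Make the single primary contrast the between-cohort difference in change from baseline to elevated IOP, that is, the group-by-IOP interaction in the mixed model, at two-sided 5%. Make cup depth, rim area and the other LC measures secondary with Holm adjustment, or label them exploratory. Report corneal measures descriptively.

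**Section 6, sample-size paragraph.** Do not carry the 80% forward as it stands. Correct the unit and meaning of 0.07, say which contrast the 80% was meant for, and restate what 115 per cohort can detect for the primary contrast: about 0.37 SD at 80% power, converted to microns if the pilot data yield an SD for the LC measure. If cup depth is kept as a surrogate, give the reason.

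**Cost.** Wording and a recalculation, with no new study procedures, although a figure in microns needs an LC SD that the plan does not contain. The stated power may look less favourable, and a cup-depth or rim-area result alone could no longer be the headline.
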